#### **4.8 Early Termination Study Visit**

We will attempt to contact all participants who withdraw from the study during the intervention phase so that we may complete any remaining assessment procedures with these participants and offer any clinical referrals if needed.

### **5 STUDY EVALUATIONS AND MEASUREMENTS**

#### **5.1 Screening Measures**

##### **5.1.1 Medical Record Review**

Medical record review for eligibility purposes and abstraction for child demographic data (baseline assessment, section 4.2, above) will occur for child participants and will include the following items. PHI marked with a \* are entered into the separate, password-protected Study ID and MRN database in REDCap used for maintaining confidentiality and storing family contact information needed for screening, enrollment, intervention procedures, and follow-up.

- Child name\*
- Age at time of enrollment
- Sex
- Race
- Ethnicity
- BMI
- Current medications
- Current diagnoses
- Current problem list
- Insurance at time of enrollment
- All family addresses on file, including zip code\*

- Caregiver names, e-mail addresses, and telephone numbers\*
- The child medical record will also be reviewed at baseline, post-intervention, and follow-up assessment periods to identify whether the child has received any behavioral health or sleep services at CHOP. We will exclude content of mental health progress notes that are not reviewable by all providers and are marked as “sensitive” (i.e., segregated mental health records). Information abstracted from the medical record in this regard will include:
  - Number of visits related to sleep concerns
  - Sleep treatment plan/recommendations
  - Sleep treatment strategies
  - After visit summary content (treatment strategies and follow-up recommendations or referrals)

### 5.1.2 Eligibility Screening Questionnaire

Caregivers will be asked questions to identify whether dyads are eligible for the study. These questions are related to child medical or neurodevelopmental conditions, medications, and the presence of child sleep problems.

## 5.2 Measures of Treatment Feasibility and Acceptability (Primary Outcomes)

- *Screening rate (feasibility)*: The study team will track the number of potentially eligible participants screened of those referred per month.
- *Recruitment rate (feasibility)*: The study team will track the number of potentially eligible participants enrolled of those screened per month.
- *Retention rate (feasibility)*: The study team will track the number of caregiver-child dyad participants who complete all study procedures following enrollment.
- *Assessment process (feasibility)*: The study team will track the number of proportion of participants who complete all assessments (pre-intervention and post-intervention) that were planned.
- *Intervention usability (feasibility)*: Study interventionists will keep records of barriers to and facilitators of the intervention content and procedures.
- *Family engagement and adherence (feasibility)*: Study interventionists will keep records of family intervention attendance, including the number of sessions that the family attended, rescheduled, and no-showed, and the number of phone calls that families completed, as well as session ratings of engagement. Study interventionists will also keep records of families’ usage of intervention strategies, based on feedback from families in-session.
- *Intervention fidelity (feasibility)*: Intervention fidelity, or the extent to which the Sleep Well! intervention is delivered as intended, will be assessed using the following two methods.
  1. Intervention sessions conducted in person, via a HIPAA-secured video platform, or via telephone will be audio-recorded and coded by a study team member. No video-recording will occur. Audio data will be provided to the Co-I/interventionist supervisor, [name], who will use this in her supervision of study interventionists. The study team will also code sessions

for fidelity purposes. Telephone check-ins between families and interventionists will not be recorded.

2. Interventionists will complete fidelity checklists that include items corresponding to the core components of Sleep Well! and to process items, including establishing trust, listening attentively, and re-directing tangential comments.
- *Treatment acceptability:* Treatment acceptability for Sleep Well! will be assessed using the following methods:
  1. Caregivers will complete the Treatment Evaluation Inventory—Short Form, a widely used measure of treatment acceptability that has been adapted for the purposes of the Sleep Well! intervention. We have also added two questions about telehealth visits to assess acceptability related to remote telephone and video intervention procedures. There will be an attention check item placed randomly within the questionnaire, which is designed to detect individuals who are quickly responding to survey questions without sufficient attention to item content. Previous research has demonstrated that the inclusion of an attention check item can increase the reliability of survey completion.
  2. Caregivers will complete the Multicultural Therapy Competency Inventory-Client Version (MTCI-CV) to assess patient's perceptions of the Sleep Well! therapist's cultural sensitivity during discussions about safe sleep.
  3. Caregivers will complete a 3-item goal attainment measure developed by the study team. Caregivers will answer each item on a 5-point Likert scale. Questions are related to caregiver perceptions of goal attainment and intervention success.
  4. Caregivers will complete an audio-recorded, open-ended qualitative interview (15-20 minutes) with questions related to aspects of the intervention that were helpful/unhelpful, how the intervention could be improved, and the acceptability of the measurement process (see interview guide uploaded with study measures).

### 5.3 Demographic and Parent and Child Behavior Measures (Secondary Outcomes and Covariates)

- *Child Demographic Information:* Child demographic information will be abstracted from the EMR (see section 5.1.1).
- *Caregiver Demographic and Family Questionnaire:* Caregivers will complete a caregiver and family demographic questionnaire at baseline. Child data will include CHOP primary care site where child receives care, whether the child attends daycare/preschool, and where the child typically sleeps. Caregiver/family data will include age, sex, race, ethnicity, highest educational level obtained, relationship to child, income, employment status, relationship status, number of times the family has moved in the last year, and information about children and adults living in the home.
- *Previous Service Use Form:* At each assessment, caregivers will complete a form related to any previous treatment for child sleep or behavior problems.
- *Brief Child Sleep Questionnaire (BCSQ):* Caregivers will complete the BCSQ to report on child sleep habits (sleep time, total sleep durations, night wakings, aspects

of the sleep environment, etc.) and the severity of any caregiver-perceived sleep problems. The BCSQ is appropriate for children ages 1-5 years and has shown good reliability and moderate correspondence with actigraphic recordings of child-sleep. There will be an attention check item placed randomly within the questionnaire, which is designed to detect individuals who are quickly responding to survey questions without sufficient attention to item content. Previous research has demonstrated that the inclusion of an attention check item can increase questionnaire reliability.

- *7-Day Daily Child Sleep Diary:* Items drawn from the BCSQ will be used to track regularity in child bedtime routines, bedtime activities, and 24-hour sleep schedule over 7 days at baseline (pre-intervention) and follow-up (post-intervention).
- *Actigraphy:* Objective child sleep will be assessed using a Philips Respironics, Inc., Actiwatch Spectrum, which is a water-resistant accelerometer device. Consistent with guidelines for the reliable and valid use of actigraph devices in children, caregivers will be instructed to keep the actigraph on their child's wrist continuously for the 7-day period at baseline and the 7-day period at follow-up, with the exception of bath time or swimming, to ensure that at least 5 days of data (to account for 2 days of missing data) are obtained. Caregivers will be asked to press an event marker at lights-off and lights-on. Actigraph data show an 85.1-88.6% agreement with polysomnography, which is the gold standard for objectively assessing sleep. Actigraph data will be analyzed using Philips Actiwatch software and scored using guidelines for young children. Actigraphs will generate daily total estimates of child sleep onset, offset, and sleep time variability. If the participant loses an Actiwatch or has difficulties with the device, the study team may choose to have the family discontinue engagement with actigraphy for subsequent data collection time points. Families will be given three options to return the actigraph to the study team after each assessment: 1) the study team will provide families with a pre-paid UPS envelope, 2) the family can coordinate a time with the study team to drop off the actigraph, or 3) the family can schedule a pick-up time with a delivery/courier service.
- *Center for Epidemiological Studies Depression Scale-Revised (CES-D-R):* Caregivers will report on their own depressed mood using the 10-item CES-D-R short form. This indicator may be used as a control variable in study analyses. The CES-D-R has shown good reliability and validity in diverse adult samples. There will be an attention check item placed randomly within the questionnaire to increase reliability in participant responses.
- *Child Behavior Checklist (CBCL):* Caregivers will complete the 99-item problem items of the Achenbach System of Empirically Based Assessment CBCL for children ages 1.5 to 5 years to report on child internalizing, externalizing, and attention problems. The CBCL has shown strong reliability and validity in large validation studies and is a widely used measure of child behavior. The CBCL will be administered via REDCap. Data will then be entered into the Achenbach System of Empirically Based Assessment (ASEBA) website for scoring, with no PHI entered into the scoring website.
- *PROMIS Sleep Disturbance Short Form:* Caregivers will report on their own perceptions of sleep quality, sleep depth, and restoration associated with sleep. This

includes perceived difficulties and concerns with getting to sleep or staying asleep, as well as perceptions of the adequacy of and satisfaction with sleep.

- *COVID-19-Related and Non-COVID-19-Related Stress Measure*: Caregivers will be asked 9 questions related to life stressors. Four questions were drawn from a measure developed by the Center for Pediatric Traumatic Stress to evaluate the impact of COVID-19 on parent and child distress. Five additional questions were developed by the study team to include non-COVID-19-related life stressors.
- *Enhanced usual care qualitative interview*: Caregivers in the enhanced usual care condition will complete an audio-recorded, semi-structured qualitative interview (15-20 minutes) at follow-up to identify their perceptions about this condition assignment and the study procedures. This information will inform future randomized trials on the intervention and the comparison condition.

## 5.4 Safety Evaluation

Participant safety will be monitored by adverse events throughout the study. Please see the Data Safety and Monitoring Plan (section 8.4.1) for further information.

# 6 STATISTICAL CONSIDERATIONS

## 6.1 Primary Endpoints

The primary endpoints are overall ratings of intervention feasibility and acceptability.

## 6.2 Secondary Endpoints

Secondary endpoints include the magnitude and direction of change in child sleep and behavior outcomes.

## 6.3 Control of Bias and Confounding

As a convenience sample, our participants may differ in important ways from those who choose not to participate in the study, which will limit the generalizability of our findings. We will mention this as a limitation of our study in any publications. In addition, in order to ensure that the subjects recruited from the study sites are representative of primary care patients presenting to these sites, we will monitor the demographics of our samples from each site to the CHOP Pediatric Research Consortium data on the demographics of patients at each site and to the demographics of primary care providers. Finally, although we will attempt to recruit subjects evenly throughout the study period, recruitment during different times of the year (i.e., various seasons) could potentially impact child sleep. We will note this as a limitation in any study publications.

## 6.4 Statistical Methods

We will examine the following primary feasibility, acceptability, and engagement and adherence outcomes through the use of descriptive statistics, which include means for continuous variables and proportions for categorical variables.

Feasibility of the research process (metrics for monitoring by internal study team):

- Screening (number of caregiver-child dyads referred and screened/month)

- Recruitment (number of caregiver-child dyads enrolled/month)
- Randomization (number of dyads eligible who enroll and are randomized/month)
- Intervention usability (interventionist-rated perceptions of intervention manual and strategies)
- Intervention adherence (interventionist-rated checklist)
- Intervention fidelity (a: interventionist self-reported checklist; b: review of the implementation of audio-recorded intervention sessions and phone calls)

Feasibility of intervention:

- Retention (number of dyads who complete intervention condition of those enrolled and number of intervention sessions/phone calls completed)
- Family engagement (interventionist-rated perceptions of family engagement in sessions and phone calls)
- Intervention acceptability (caregiver-rated Treatment Evaluation Inventory – Short Form and the Multicultural Therapy Competency Inventory- Client Version [cultural humility])
- Assessment process (number of planned assessments that are completed)

Prior to quantitative data analysis, we will examine baseline equivalency of the randomized groups, attrition and missing data. Baseline equivalence will consist of chi-square and grouped t-tests analyses comparing randomized groups on demographic characteristics and baseline outcomes. We will conduct an attrition analysis consisting of chi-square and grouped t-tests comparing the proportion of participants who fail to complete surveys; the independent variables will include intervention condition and demographic characteristics. We will also explore missing data due to item non-response among participants who completed the surveys. If missing data due to item non-response is non-trivial (greater than 5%), we will conduct a missing data analysis using the same analytic approach for the attrition analysis.

For qualitative interview data, transcribed interviews will be coded by study team members using an iterative process that begins with open coding, codebook development and refinement, and consensus regarding the codes. We will use an integrated approach, with a priori codes based on prior work and themes emerging from the data. Once a stable codebook is developed, approximately 20% of the data will be double coded for reliability purposes (weighted kappa). Separate codebooks may be developed for the Sleep Well! participant interviews and for the enhanced usual care condition interviews. We will also explore how themes from the intervention group vary by quantitative caregiver-reported outcome data (e.g., sleep problem perception) and family factors (e.g., shiftwork). We will also examine variation using this method for the usual care group interviews.

Data analysis for the secondary sleep outcomes (below) will include (1) the application of mixed effects growth models, and (2) generating effect sizes, as follows.

- (1) Mixed effects linear growth models will also be applied to compare overall change in continuous outcomes between groups from pre-intervention to follow-up using an intent to treat approach with maximum likelihood estimation. Individual variability in the outcomes from pre-intervention through the follow-up assessments will be predicted by a two-level fixed effect condition variable (coded 0 for enhanced usual

care and 1 for intervention), a time variable with the intercept defined as the pre-intervention assessment and weeks between this assessment and last follow-up, and the group  $\times$  time interaction. Models will account for random effects (intercept, time) and fixed effects (group, and time by group). The time by intervention group interaction identifies whether there is a significant between-group difference in change since pre-intervention. Categorical outcomes will be modeled as mixed-effects growth models with maximum likelihood and a logit link. Model parameters include those described for the continuous models and a threshold parameter at each timepoint. Any sleep and behavior outcomes that are significantly different by group at pre-intervention will be included as covariates in all models.

- (2) Effect sizes for the magnitude of group differences will be drawn from the mixed effects models. The effect size for the condition  $\times$  time interaction is equivalent to Cohen's d-statistic. For categorical outcomes, percent change in the odds for the condition  $\times$  time interactions are provided as a measure of effect size.

Secondary sleep outcomes for these analyses will be drawn from the caregiver-rated Brief Child Sleep Questionnaire (BCSQ) and actigraphy (objective sleep measurement) and will include:

- Child sleep problems (BCSQ)
- Child bedtime resistance (also called "bedtime difficulties" BCSQ)
- Child sleep onset latency (BCSQ)
- Child night awakenings (frequency and duration BCSQ)
- Child sleep quality (BCSQ)
- Child total (BCSQ) and nighttime sleep duration (BCSQ and sleep onset to offset for actigraphy)

To examine secondary child behavior outcomes, we will examine change by group over time from pre-intervention to follow-up, exactly as described for the sleep outcomes (see above).

Secondary behavior outcomes drawn from validated the following validated clinical measures include:

- Child externalizing problems composite T-score (Child Behavioral Checklist for ages 1.5-5 years)
- Child internalizing problems composite T-score (Child Behavioral Checklist for ages 1.5-5 years)

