### **2.2 Secondary Objectives (or Aim)**

The secondary objectives are to:

- Compare Sleep Well! to enhanced usual care on objective and caregiver-reported child sleep over post-intervention and follow-up
- Explore the effects Sleep Well! on child behavior outcomes over post-intervention and follow-up.

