### **8.4.2 Risk Assessment**

Risks of participating in this study are not greater than minimal. There are no known physical or legal risks to participating in the study intervention. Potential risks are as follows:

---

Families will be asked to participate in **actigraphy assessment** at pre- and post-intervention and at follow-up. There are no risks with wearing an actigraph, which is the size and shape of a small wristwatch, though some participants may consider it a minor inconvenience. To ensure that actigraphs are clean and do not increase risk for transmission of COVID-19 and other viruses, each actigraph will be sanitized prior to being provided to families and immediately upon return of the device. We will also provide families with wipes for sanitizing the device upon request.

Families may experience **continued child sleep problems** following the intervention phase or during the enhanced usual care condition. If families who participated in Sleep Well! report continued child sleep concerns at post-intervention, we will refer families to the child's primary care pediatrician for further guidance and potential referral to the CHOP Sleep Center or other behavioral health services, which is the current standard of care for managing child sleep problems. Families in the enhanced usual care condition will similarly be referred to their pediatrician for further guidance and potential referrals if they experience continued child sleep problems.

Although we are not asking caregivers to report on any instances of **child abuse or neglect**, should a caregiver or child spontaneously disclose this information to us during the study procedures or intervention phase, we will file a Department of Human Services report in this regard. Based on standard behavioral health practices within the CHOP system, these procedures are likely to be effective in the case that additional behavioral health treatment and/or risk assessment are necessary.

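### The single linear group-by-time slope in section 6.4 cannot separate the post-intervention effect from the follow-up effect, and it misstates the former unless the difference grows linearly to follow-up

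*Combined protocol and SAP*

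**What the plan says.** Section 6.4 gives one model for the continuous sleep outcomes: "Mixed effects linear growth models will also be applied to compare overall change in continuous outcomes between groups from pre-intervention to follow-up". Time is "a time variable with the intercept defined as the pre-intervention assessment and weeks between this assessment and last follow-up". The test is one coefficient: "The time by intervention group interaction identifies whether there is a significant between-group difference in change since pre-intervention". Section 6.4 also states: "Effect sizes for the magnitude of group differences will be drawn from the mixed effects models", and equates the condition-by-time effect with Cohen's d without naming a time at which the slope is evaluated. The behaviour outcomes follow the same method. No visit-specific, piecewise or categorical-time contrast is planned.

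The secondary objective in section 2.2 is to "Compare Sleep Well! to enhanced usual care on objective and caregiver-reported child sleep over post-intervention and follow-up". The Abstract describes the secondary outcomes as direction and magnitude at both of those times.

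Section 3.1 places the 6 to 8 weeks of Sleep Well! before a post-intervention visit at week 9 to 16, and the follow-up visit 6 to 8 weeks after that (week 15 to 24). No sessions are scheduled in between.

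On other care, section 8.4.2 says: "If families who participated in Sleep Well! report continued child sleep concerns at post-intervention, we will refer families to the child's primary care pediatrician". For controls it says: "Families in the enhanced usual care condition will similarly be referred to their pediatrician for further guidance and potential referrals". Section 3.1 already directs controls to their pediatrician when they receive the handout, and section 4.3.3 lets them consult their physician during the control phase. On recording such care, section 5.3 says: "At each assessment, caregivers will complete a form related to any previous treatment for child sleep or behavior problems". Table 1 agrees, but the follow-up list in section 4.5 omits that form.

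**The concern.** The schedule has a treated phase and then an untreated one. After the sessions end, the between-arm difference may hold, fade or go on growing, and the plan states no expected course. A straight line forces the same weekly gain before and after the post-intervention visit. If the true course bends, the slope averages over the bend and matches neither visit exactly.

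The sleep and behaviour outcomes are secondary, and the primary endpoints are descriptive feasibility and acceptability measures. The slope still matters, because section 6.5 names estimation of effect sizes for a later full-scale trial as the main purpose. A planner would need to know whether the reported d is an end-of-treatment effect or a maintained effect. As written, it is not identified as either.

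**Working it through.** **The plan's own figure.** Section 6.5 enrols 80 and expects 15% attrition: 80 × 0.85 = 68, which reproduces. The stated power above 80% for 0.5 SD does not follow from those inputs alone. With 34 per arm (1:1 assumed) and two-sided 0.05 (assumed), an unadjusted comparison has 53–54% power. A covariate–outcome correlation of about 0.69 would be needed, and none is stated. That calculation uses covariate-adjusted linear regression, so it does not describe the slope in section 6.4.

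**Inputs.** Post-intervention visit t1 = 9 to 16 weeks and follow-up t2 = t1 + 6 to 8 weeks (section 3.1), with baseline at week 0. The true group difference in change is 0 at baseline, D at t1 and f·D at t2. D and f are assumptions; D = 0.5 SD is taken from section 6.5.

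**Formula.** With complete, balanced data at three visits and a random intercept and slope, the fixed slope difference equals the least-squares slope through the visit differences:

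slope = Σ(t − t̄)·d / Σ(t − t̄)²

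The implied effect is slope × t1 at the post-intervention visit and slope × t2 at follow-up.

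**Mid-window example, weeks 0, 12.5, 19.5.** t̄ = 32/3 = 10.667. The deviations at the two later visits are 1.833 and 8.833. The denominator is 12.5² + 19.5² − 32²/3 = 195.17.

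- Effect holds (f = 1): slope = (1.833 + 8.833)D/195.17 = 0.05465D. At week 12.5 this is 0.68D, so 0.50 SD reads as 0.34 SD. At week 19.5 it is 1.07D against a true 1.00D.
- Effect halves (f = 0.5): slope = (1.833 + 4.417)D/195.17 = 0.03202D. At week 12.5 this is 0.40D (0.20 SD). At week 19.5 it is 0.62D against a true 0.50D.

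**Range over the section 3.1 windows, as a share of D.**

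| True course | Slope read at t1 (truth 1) | Slope read at t2 | Truth at t2 |
|---|---|---|---|
| Halves, f = 0.5 | 0.28–0.50 | 0.53–0.68 | 0.50 |
| Holds, f = 1 | 0.54–0.78 | 1.02–1.08 | 1.00 |
| Linear growth, f = t2/t1 = 1.38–1.89 | 1.00 | 1.38–1.89 | 1.38–1.89 |
| Doubles, f = 2 | 1.06–1.36 | 1.87–2.00 | 2.00 |

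Read at t1, the slope is too low when f is below t2/t1 and too high when f is above it. Visit-specific contrasts return D and f·D without bias in every row.

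**Power at weeks 12.5/19.5.** Assumptions: D = 0.5 SD, 34 per arm, within-child correlation 0.4–0.7, random-slope SD 0–0.02 per week. The change to post-intervention has 45–76% power whatever happens later. The slope has 48–82% if the effect holds, 20–39% if it halves and 80–99% under linear growth. In the linear case, with correlation 0.5 and no random slope, the follow-up contrast is 0.5 × 19.5/12.5 = 0.78 SD with standard error √(2/34) = 0.243. Its power is then about 90%, the same as the slope's after rounding.

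**Sensitivity.**
- If study weeks count from screening, t1 could be about 8 weeks. With t2 = 16, the plateau share at t1 is 0.50.
- The mid-point sleep survey is given to the intervention arm only, and section 6.4 does not say whether it enters the model. If it does (week 4 assumed), the mid-window plateau share ranges over 0.49–0.77, depending on how early the effect appears.
- These figures are for continuous outcomes. Categorical outcomes have the same one-slope structure on the log-odds scale, which was not computed.

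**The case against.** The strongest defence is that section 6.4 asks about overall change to follow-up, and time is defined up to the last follow-up, so d would naturally be read there. On that reading an effect that holds is reported at 1.02–1.08 of its true follow-up size, and the slope loses no power. A model in actual weeks also uses the wide visit windows better than visit codes do. The wording of section 2.2 can be read as one overall comparison.

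Much of this stands. A reader might infer that the plan understates the post-intervention effect. The documents do not support that as a flat statement: it needs a difference that grows less than linearly after the post-intervention visit and a slope read at that visit, and they settle neither. The defence does not remove the main point. The Abstract names magnitude at both times, one slope cannot supply both, and the read-out time remains unstated.

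A reader might also infer that referral after the post-intervention visit lets controls catch up. That is not supported either. Controls are directed to their pediatrician from the start, and only the Sleep Well! referral is tied to post-intervention. Later care in the intervention arm would widen the difference rather than close it.

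Nor does section 4.5 leave the EMR as the only record of later care in both arms. It lists a sleep-services interview for controls.

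**Conclusion.** The point holds in conditional form. That one slope cannot separate the two named effects is certain from the text. The size of the misstatement depends on a course the plan does not state. Read at the post-intervention visit, the shortfall is 22–46% if the effect holds and 50–72% if it halves. There is none under linear growth, and an excess of 6–36% if the effect doubles by follow-up. Read at follow-up, the figure is 2–8% high if the effect holds and 6–36% high if it halves (0.53/0.50 to 0.68/0.50). Power suffers only if the effect fades. These results assume complete data, three visits common to both arms and the section 3.1 timing. The outcomes are secondary, so this is a worthwhile, inexpensive improvement rather than a threat to the primary endpoints.

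The service-use point is a separate inconsistency. With section 4.5 as written, controls have the services interview and the EMR review at follow-up, while intervention families have the EMR review alone. Section 5.1.1 limits that review to services received at CHOP. Section 4.3.3 allows controls external referrals, and section 8.4.2 does not confine the other behavioural-health services for Sleep Well! families to CHOP.

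**What to change.** - In section 6.4, add group contrasts from the same mixed model, with categorical or piecewise time, for change to post-intervention and change to follow-up. Standardise each as d at its own visit and name these as the estimates for planning the next trial.
- Keep the linear slope as a secondary summary. State the time at which it is converted to d, and whether the intervention-only mid-point data enter the model.
- Describe the follow-up contrast as including any services received by then. Do not label the post-intervention contrast as free of referral, because controls may already have sought care.
- Reconcile section 4.5 with Table 1 and section 5.3 on the caregiver service-use form, and tabulate services by arm beside the follow-up contrast.
- Reconcile the follow-up timing, since any conversion to d depends on it: section 3.1 counts 6 to 8 weeks from the post-intervention assessment, section 4.5 counts them from the end of the intervention phase, and Table 1 says 2–3 months. Reconcile also the actigraphy schedule, which has three time points in Table 1 but only baseline and follow-up in section 5.3. The objective-sleep contrast at post-intervention needs the three.

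The cost is wording and one more group-by-time parameter, with no data beyond Table 1. Coding time by visit gives up some actual-week timing within wide windows; a piecewise form keeps it. If change is truly linear, the follow-up contrast loses very little power against the slope, but the post-intervention contrast targets a smaller effect and has less (45–76% against 80–99%).
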